3.1.4 PK and ADA data

Blood samples will be regularly collected and submitted for PK and anti-drug antibody (ADA) assays. Support for these assays will be provided by MacroGenics. Total and ADC PK assays as well as ADA assays will be performed on the serum. Samples for PK data will be collected pre- and post-infusion as

well as on day 15 of cycles 1 and 2 then pre- and post-infusion for cycles 3 through 5 as well as every 3 cycles for cycles 6 through 12. ADA assays will be performed on samples collected pre-infusion as well as on day 15 of cycle 1 then pre-infusion for cycles 2 through 5 and every 3 cycles for cycles 6 through 12. PK and ADA testing will be obtained at the EOTV. PK and ADA testing may be performed at the time of any IRR.

Table 2. PK and ADA collection schedule

| Cycle | Day | Timepoint | Window | PK: Total and ADC (serum) | ADA: (serum) |
|------------------|-----|-----------------|---------|------------------------------------|-----------------|
| 1 | 1 | Pre-infusion | N/A | X | X |
| 1 | 1 | End of infusion | +10 min | X | |
| 1 | 15 | Day 15 | N/A | X | X |
| 2 | 1 | Pre-infusion | N/A | X | X |
| 2 | 1 | End of infusion | +10 min | X | |
| 2 | 15 | Day 15 | N/A | X | |
| 3, 4, and 5 | 1 | Pre-infusion | N/A | X | X |
| 3, 4, and 5 | 1 | End of infusion | +10 min | X | |
| 6, 9, and 12 | 1 | Pre-infusion | N/A | X | X |
| 6, 9, and 12 | 1 | End of infusion | +10 min | X | |
| IRR ^a | N/A | N/A | N/A | X | X |
| EOTV | N/A | EOTV | N/A | X | X |

Note: Actual start of infusion times, EOI times, and PK/ADA sample collection times will be recorded on the eCRFs. Do not collect PK samples from infusion port. Pre-infusion PK samples may be collected before start of infusion on visit day (dosing day) or day before infusion. When collecting multiple samples, collect the PK sample first.

^aPK and ADA samples may be obtained at additional time points in participants who experience signs and symptoms of IRR. Samples should be obtained as soon as possible after onset of IRR, if feasible.

3.1.5 Tumor biopsies

A tissue biopsy will be obtained prior to initiation of study treatment with an optional biopsy at the time of progression. If biopsy is not considered safe and medically feasible by the investigator, the patient may be approved for enrollment after consultation the principal investigator. In this case, we will obtain archival tissue if available. Expression of B7-H3 and other immune markers on tumor tissue will be assessed using Imaging Mass Cytometry (IMC; Fluidigm platform) and correlated with treatment outcomes such as ORR, PFS, and OS. Imaging Mass Cytometry platform is capable of simultaneous detection of up to 40 protein markers including B7-H3 at subcellular resolution in fixed tissues sections. Imaging Mass Cytometry is available through the Histopathology & Tissue Shared Resource (HTSR) at Georgetown Lombardi Comprehensive Cancer Center. Samples are analyzed using ilastik and Cell Profiler software (**Figure 4**) for cell mask segmentation, allowing to identify individual cells in the tissue based on staining of the nuclei (DAPI staining) and plasma membrane. This analysis is followed by evaluating the expression of the markers using HistoCAT software. An optional tumor biopsy at the time of disease progression will be obtained after radiographic progression prior to start of new anti-cancer treatment, if any. These samples will enable analysis of tumor tissue biomarkers related to resistance, disease progression, and clinical benefit of the study treatment. If sufficient tissue is available after IMC analysis, next generation sequencing (NGS) may be performed to understand the correlation between genomic findings and response to treatment. Please refer to the lab manual for full details.

[figure not shown]

Figure 4. High dimensional data analysis of images of NSCLC tissue sample. (A) tSNE (t-distributed stochastic neighbor embedding) plot showing multidimensional data. (B) Phenograph clustering analysis representing phenotypic similarities between cells. (C) Overlay images of MET, VEGF and VISTA on histoCAT. (D) Overlay of the markers highlighting phenograph cluster 1 (turquoise). Immune checkpoints including B7-H3 (E), and fibroblast/stroma (F).

3.1.6 Blood based correlative studies

In collaboration with [name] at the Tisch Cancer Institute at Mount Sinai Health System, we plan to analyze extracellular vesicle (EV) B7-H3 expression on day 1 of cycle 1, on day 1 of cycle 3, and at the time of progression. Peripheral blood will be collected into EDTA Vacutainer® tubes. Blood samples will be centrifuged at 2,000 × g for 15 minutes, and plasma will be isolated and frozen at -80 °C. Blood samples will be analyzed in a batch. Following the last recommendations of the International Society of Extracellular Vesicles (ISEV), EVs will be characterized by nanoparticle tracking analysis (NTA), transmission electron microscopy (TEM), and western blot following standardized

methodology established at [name] laboratory (de Miguel-Perez et al. 2022). The baseline EV expression of B7-H3 and the EV B7-H3 dynamics will be correlated with treatment outcomes. Please refer to the lab manual for full details.

3.1.7 Safety assessment

Safety will be closely monitored by assessing for the frequency of severe adverse events and unexpected adverse events, including adverse events of special interest (AESIs). Georgetown University institutional review board (IRB) and data safety monitoring committee (DSMC), in conjunction with the study Principal Investigator (PI), will be responsible for monitoring the safe conduct of this study in real time. Regular DSMC meetings will take place approximately every 3 months or more frequently and resulting recommendations will be forwarded to the IRB, in addition to the PI (as study sponsor). If the DSMC recommends a study change for patient safety or efficacy reasons, it is the responsibility of the PI to implement said changes expeditiously. In the unlikely event of disagreement, the trial PI, DSMC Chair and LCCC Deputy Director will be responsible for determining a mutually agreed upon decision. Should the DSMC recommend trial closure for any reason, the recommendation will be reviewed by the LCCC Deputy Director. Authority to close a trial for safety concerns lies with the IRB in concert with DSMC and LCCC Deputy Director input. No interim analyses specifically for safety are planned as part of this study.

3.2 END OF STUDY AND LENGTH OF STUDY

The end of this study is defined as the date when the last patient, last visit (LPLV) occurs or the required number of events for the final analysis of ORR has occurred or all patients meet one of the following criteria: patient has experienced a PFS event, patient has become lost to follow-up, patient has withdrawn consent, or patient has completed at least 24 months of follow-up after study treatment initiation. The end of the study is expected to occur approximately 1 year after the last patient is enrolled. In addition, the principal investigator may decide to terminate the study at any time. The total length of the study, from screening of the first patient to the end of the study, is expected to be approximately 3 years.

3.3 RATIONALE FOR STUDY DESIGN

3.3.1 Rationale for MGC018 dose and schedule

MGC018 will be administered at a dose of 2.0 mg/kg every 28 days continuously until completion of 8 cycles, disease progression, or unacceptable toxicity. The dose was selected on the basis of available clinical pharmacokinetics, efficacy, and safety data from the open label, dose escalation CP-MGC018-01 phase I study. Specifically, the dosing was 3.0 mg/kg every 21 days in the prior phase 1 dose escalation study of MGC018 (Shenderov et al. 2021). However, there has been subsequent evidence of increased neutropenia and hand-foot syndrome at this dose, and doses of 2.0 mg/kg every 28 days and 2.7 mg/kg every 28 days are being investigated in the phase 2 and 3 MGC018 trials. For patients who require a dose-reduction, the first reduction would be to 1.5 mg/kg every 28 days and a second reduction to 1.0 mg/kg as needed. Please refer to the MGC018 IB for details.

3.3.2 Rationale for ORR as primary endpoint

In this study, the primary endpoint of efficacy will be investigator-assessed ORR as determined by RECIST v1.1 with tumor imaging assessments obtained every 2 cycles. As this is a small phase 2 study to evaluate the efficacy of a novel therapy in a treatment refractory patient population, ORR was chosen in order to make an early determination for signal of efficacy that could then be used to warrant larger scale clinical trials powered for OS/PFS or, given the modified Simon 2-stage design, early study closure for futility if no efficacy signal is observed. Given the low historical ORR to chemotherapy in relapsed or refractory patients with ES-SCLC, a rapid estimation of response utilizing ORR will also be important as it will enable patients with robust functional status who experience disease progression on this trial seek additional treatments either in a clinical trial or standard of care setting.

3.3.3 Rationale for PK and ADA assessments

The optimal dosing of MGC018 is still being determined. While the dose 3.0 mg/kg every 21 days was used in the phase 1 trial, this dose was subsequently found to be associated with increased rates of neutropenia and hand-foot syndrome. The use of 2.0 mg/kg every 28 days are currently being investigated in phase 2 and 3 trials. Collection of PK and ADA data for patients receiving 2.7 mg/kg every 28 days, as well as for those who require a dose-reduction to 2.0 mg/kg every 28 days, will be useful in elucidating the optimal regimen.

3.3.4 Rationale for biomarker assessments

Early clinical studies have shown that efficacy of MGC018 in patients with non-small cell lung cancer (NSCLC) and metastatic castration resistant prostate cancer (mCRPC) can be seen across varying levels of B7-H3 expression (Shenderov et al. 2021). This is suspected to be likely from bystander killing of neighboring tumor cells which has been demonstrated *in vivo* (Scribner et al. 2020). However, this has not been studied in ES-SCLC, and current clinical data regarding correlation between MGC018 efficacy and B7-H3 expression is still early. In this study, we will assess expression of B7-H3 on tumor tissue obtained prior to study initiation and correlate with treatment outcomes. Furthermore, blood-based biomarkers including exosome analysis in collaboration with [name] at the Tisch Cancer Institute at Mount Sinai Health System will be analyzed and correlated with treatment outcomes.

4. MATERIALS AND METHODS

4.1 PATIENTS

Approximately 17 patients with relapse or refractory ES-SCLC will be enrolled in this study.

4.1.1 Inclusion criteria

Patients must meet the following criteria for study entry:

- 1) Age \geq 18 years at time of signing ICF
- 2) Ability to comply with the study protocol, in the investigator's judgment.

- 3) Histologically or cytologically confirmed advanced small cell lung cancer that is not amenable to definitive therapy. Patients with *EGFR*-mutant NSCLC that has transformed to SCLC will be allowed.
 - 4) Disease progression during or following treatment with platinum-based chemotherapy.
 - a) Patients could have received any number of therapies for relapsed or progressive disease.
 - 5) Measurable disease per RECIST v1.1
 - 6) ECOG Performance Status of 0-2
 - 7) Adequate hematologic and end-organ function, defined by the following laboratory test results, obtained within 14 days prior to initiation of study treatment:
 - a) ANC $\geq 1.0 \times 10^9/L$ ($1000/\mu L$) without granulocyte colony-stimulating factor support
 - b) Platelet count $\geq 100 \times 10^9/L$ ($100,000/\mu L$) without transfusion
 - c) Hemoglobin ≥ 80 g/L (8 g/dL)
 - (1) Patients may be transfused to meet this criterion.
 - d) AST, ALT, and alkaline phosphatase (ALP) $\leq 2.5 \times$ upper limit of normal (ULN), with the following exceptions:
 - (1) Patients with documented liver metastases: AST and ALT $\leq 5 \times$ ULN
 - (2) Patients with documented liver or bone metastases: ALP $\leq 5 \times$ ULN
 - e) Serum bilirubin $\leq 1.5 \times$ ULN with the following exception:
 - (1) Patients with known Gilbert disease: serum bilirubin $\leq 3 \times$ ULN
 - f) Creatinine clearance ≥ 30 mL/min (calculated using the Cockcroft-Gault formula, see Appendix 2)
 - g) For patients not receiving therapeutic anticoagulation: INR and aPTT $\leq 1.5 \times$ ULN
- NOTE: Screening labs that are performed outside the 14-day window for eligibility criteria may be repeated on C1D1 to verify the subject meets eligibility requirements.
- 8) Ability to understand and the willingness to sign a written informed consent document.
 - 9) Availability of pre-treatment tumor tissue via a biopsy. If biopsy is not considered safe and medically feasible by the Investigator, the patient may be approved for enrollment after consultation with the Principal Investigator.
 - 10) For women of childbearing potential: agreement to remain abstinent (refrain from heterosexual intercourse) or use contraceptive methods, and agreement to refrain from donating eggs, as defined below:
 - (1) Women must remain abstinent or use contraceptive methods with a failure rate of $< 1\%$ per year during the treatment period and for 6 months after the final dose of study treatment. Women must refrain from donating eggs during this same period.
 - (2) A woman is considered to be of childbearing potential if she is postmenarchal, has not reached a postmenopausal state (≥ 12 continuous months of amenorrhea with no identified cause other than menopause), and has not undergone surgical sterilization (removal of ovaries and/or uterus). The definition of childbearing potential may be adapted for alignment with local guidelines or requirements.

- (3) Examples of contraceptive methods with a failure rate of < 1% per year include bilateral tubal ligation, male sterilization, hormonal contraceptives that inhibit ovulation, hormone-releasing intrauterine devices, and copper intrauterine devices.
 - (4) The reliability of sexual abstinence should be evaluated in relation to the duration of the clinical trial and the preferred and usual lifestyle of the patient. Periodic abstinence (e.g., calendar, ovulation, symptothermal, or postovulation methods) and withdrawal are not adequate methods of contraception.
- 11) For men: agreement to remain abstinent (refrain from heterosexual intercourse) or use contraceptive measures, and agreement to refrain from donating sperm, as defined below:
- (1) With a female partner of childbearing potential who is not pregnant, men who are not surgically sterile must remain abstinent or use a condom plus an additional contraceptive method that together result in a failure rate of < 1% per year during the treatment period and for 90 days after the final dose of MGC018. Men must refrain from donating sperm during this this same period.
 - (2) With a pregnant female partner, men must remain abstinent or use a condom during the treatment period and 90 days after the final dose of MGC018 to avoid potential exposure to the embryo.
 - (3) The reliability of sexual abstinence should be evaluated in relation to the duration of the clinical trial and the preferred and usual lifestyle of the patient. Periodic abstinence (e.g., calendar, ovulation, symptothermal, or postovulation methods) and withdrawal are not adequate methods of contraception.

ii) Exclusion criteria

Patients who meet any of the following criteria will be excluded from study entry:

- 1) Patients with treated CNS metastases are eligible if they are symptomatically stable while off steroid therapy for a minimum of 7 days
- 2) Symptomatic leptomeningeal disease. Patients with asymptomatic treated or untreated leptomeningeal disease could be enrolled provided that all other protocol-defined criteria are met.
- 3) Patient who are receiving any other investigational agents
- 4) Major surgical procedure, other than for diagnosis, within 4 weeks prior to initiation of study treatment, or anticipation of need for a major surgical procedure during the study
- 5) Diagnosis of another malignancy. However, patients with prior or concurrent malignancy whose natural history or treatment does not have the potential to interfere with the safety or efficacy assessment of the investigational regimen are eligible for this trial.
- 6) Evidence of pleural and/or pericardial effusion. A small and/or asymptomatic effusion is not exclusionary.
- 7) Any other disease, metabolic dysfunction, physical examination finding, or clinical laboratory finding that, in the view of the investigator, contraindicates the use of an investigational drug, may affect the interpretation of the results, or may render the patient at high risk from treatment complications.
- 8) Pregnancy or breastfeeding, or intention of becoming pregnant during study treatment or within 6 months after the final dose of study treatment.

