| Neutropenia, Grade 1 or 2 | 
 • No specific therapy required • MGC018 should not be given to participants with neutrophil counts ≤ 1500 cells/mm³ • Consider dose reduction of MGC018 |
| Neutropenia, Grade 3 | 
 • Hold MGC018 until recovery to \leq grade 1 • Monitor neutrophil counts weekly until recovery to \leq grade 1 • Discontinue MGC018 if not recovered to \leq grade 1, within 21 days • Restart MGC018 if recovered to \leq grade 1 within 21 days. • On resuming MGC018, reduce dose by one dose level after first and second occurrences • Discontinue MGC018 after third occurrence |
| Neutropenia, Grade 4 | 
 • Hold MGC018 until recovery to \leq grade 1 • Monitor neutrophil counts weekly until recovery to \leq grade 1 • Discontinue MGC018 if not recovered to \leq grade 1, within 21 days • Restart MGC018 at one or two level dose reduction if recovered to \leq grade 1 within 21 days. • On resuming MGC018 reduce dose by two dose levels after first occurrence • Discontinue MGC018 after second occurrence |
| Thrombocytopenia, Grade 1 | 
 • No specific therapy required • Consider dose reduction of MGC018 |

| | |
|-----------------------------------|--|
| Thrombocytopenia, Grade 2 or 3 | 
 • Hold MGC018 until recovery to \leq grade 1 • Monitor platelet counts weekly until recovery to \leq grade 1 • Restart MGC018 with one level dose reduction if recovered to \leq grade 1 • Reduce dose by one dose level on resumption after second and third occurrences • Discontinue MGC018 after fourth occurrence • Discontinue MGC018 if not recovered to \leq grade 1 within 21 days. |
| Thrombocytopenia, Grade 4 | 
 • Hold MGC018 until recovery to \leq grade 1 • Monitor platelet counts weekly until recovery to \leq grade 1 • Restart MGC018 with one or two level dose reduction if recovered to \leq grade 1 • Discontinue MGC018 if not recovered to \leq grade 1 within 21 days. • On resuming MGC018 reduce dose by two dose levels after first occurrence • Discontinue MGC018 after second occurrence |
| Anemia, Grade 1 | 
 • No specific therapy required |
| Anemia, Grade 2 | 
 • Consider iron replacement therapy, erythropoiesis stimulating agent |

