4.4.5 Tumor response evaluations

Any evaluable or measurable disease must be documented at screening and re-assessed at each subsequent tumor evaluation. Tumor assessments performed as standard of care prior to obtaining informed consent and within 28 days prior to initiation of study treatment do not have to be repeated at screening. Measurable disease is a requirement for study inclusion and response will be assessed by the investigator per RECIST v1.1 at baseline. Patients will undergo tumor assessments every 2 cycles while on study until radiographic disease progression per RECIST v1.1 or loss of clinical benefit as determined by the investigator. Tumor assessments should be performed during the last week of the cycle and before the start of treatment in the next cycle (see Appendix 1). At the investigator's discretion, tumor assessments may be repeated at any time if progressive disease is suspected.

Screening assessments must include CT or magnetic resonance imaging (MRI) scans (with IV contrast unless contraindicated) of the chest, abdomen, and pelvis. If a positron emission tomography (PET)/CT scan is performed, the CT portion of the study must be consistent with the standards of a full-contrast diagnostic CT scan unless IV contrast is contraindicated. A CT scan with contrast or MRI scan of the head must be done at screening to evaluate for the presence of CNS metastases in all patients (MRI preferred). An MRI scan of the head is required to confirm or refute the diagnosis of CNS metastases at baseline in the event of an equivocal CT scan. At the investigator's discretion, other methods of assessment of measurable disease as per RECIST v1.1 may be used.

All measurable and evaluable lesions identified at baseline should be re-assessed at each subsequent tumor evaluation. The same radiographic procedures used to assess disease sites at screening should be used for subsequent tumor assessments (e.g., the same contrast protocol for CT scans). Stable brain metastases must be evaluated with each subsequent tumor assessment with the same radiographic procedure as the baseline study. Patients without brain metastases do not need brain scans for subsequent on-treatment tumor assessment unless clinically warranted or part of standard-of-care treatment.

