4.4.6 Laboratory, biomarker, and other biological samples

Samples for the following laboratory tests must be reviewed prior to dosing. See Appendix 1 for specifics related to which lab tests are required at specific time points during study ("screening" vs "on treatment", etc.):

- Hematology: WBC count, RBC count, hemoglobin, hematocrit, platelet count, and differential count (neutrophils, eosinophils, basophils, monocytes, lymphocytes, other cells).
- Chemistry panel (serum or plasma): bicarbonate or total carbon dioxide (if considered standard of care for the region), sodium, potassium, chloride, glucose, BUN or urea, creatinine, total protein, albumin, phosphorus, calcium, total bilirubin, alkaline phosphatase, ALT, and AST.
- Coagulation: INR, and aPTT (screening only).
- Thyroid function testing: thyroid-stimulating hormone (TSH), free triiodothyronine (T3) (or total T3 for sites where free T3 is not performed), and free thyroxine (also known as T4) at screening only. Repeat thyroid function testing as clinically indicated.

- Pregnancy test

All women of childbearing potential will have a serum pregnancy test at screening, and during the study, urine pregnancy tests will be performed at every cycle and after study treatment is discontinued. If a urine pregnancy test is positive, it must be confirmed by a serum pregnancy test.

A woman is considered to be of childbearing potential if she is postmenarchal, has not reached a postmenopausal state (≥ 12 continuous months of amenorrhea with no identified cause other than menopause), and has not undergone surgical sterilization (removal of ovaries and/or uterus).

The following samples will be sent to the PI or a designee for analysis or banked for subsequent analysis:

- Peripheral blood to be obtained on day 1 of cycle 1, day 1 of cycle 3, and at progression
- Prior to treatment initiation, tumor tissue will be obtained following progression on most-recent therapy for determination of biomarker status including exploratory correlative analyses. Please refer to the lab manual for details. **If a biopsy is not feasible and/or safe, it may be waived after discussion with the principal investigator.** In this case, we will obtain archival tissue if available.

For sampling procedures, storage conditions, and shipment instructions, see the laboratory manual.

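### The CNS item in the exclusion list is worded as an eligibility rule and leaves untreated parenchymal metastases unaddressed, and the ANC entry threshold conflicts with the Table 13 dosing threshold

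*Combined protocol and SAP*

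**What the plan says.** **CNS disease.** The exclusion list in section 4.1 opens with "Patients who meet any of the following criteria will be excluded from study entry". Item 1 is then "Patients with treated CNS metastases are eligible if they are symptomatically stable while off steroid therapy for a minimum of 7 days". Two other items bear on the question:

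- Item 2: "Symptomatic leptomeningeal disease. Patients with asymptomatic treated or untreated leptomeningeal disease could be enrolled provided that all other protocol-defined criteria are met".
- Item 7 is a general investigator-judgement clause, covering among other things findings that "may render the patient at high risk from treatment complications".

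Section 4.4.5 requires a contrast CT or an MRI of the head at screening in all patients, to look for CNS metastases. It later refers to following stable brain metastases on study.

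**ANC.** Inclusion 7a requires an ANC of at least 1000/µL "without granulocyte colony-stimulating factor support". In section 4.2.3.2, the Table 13 row for grade 1 or 2 neutropenia says "MGC018 should not be given to participants with neutrophil counts" at or below 1500 cells/mm³. Section 4.4 allows dosing only when the clinical assessment and local laboratory values are acceptable, and applies this before each dose. It also says that laboratory tests done within 14 days of Cycle 1 Day 1 need not be repeated.

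**Coagulation.** Inclusion 7g sets limits for INR and aPTT in patients not on therapeutic anticoagulation, and section 4.4.6 lists both tests at screening. The laboratory row of the screening calendar (Appendix 1, Table 1) does not include them.

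**The concern.** Eligibility criteria define the population in which the response rate is estimated, and here they also protect patients. Item 1 points the opposite way from its lead-in, and the commonest question after a positive head scan, what to do with untreated disease, has no written answer. Section 9.2 does not allow requests to waive eligibility criteria, so a site cannot put the wording right informally.

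The ANC rules can place a patient in a position where one binding passage says enrol and another says do not treat. The patient is then either dosed against Table 13 or accrued without being dosed. In the second case the patient is outside the primary efficacy set, which section 6.2 limits to those with at least one dose. With at most 17 patients and rejection at 3 responses, each patient counts.

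**Working it through.** **1. CNS criterion, by type of patient.** Each row compares the literal reading of item 1 under its lead-in with the reading by evident intent.

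| Patient | Literal reading | Reading by intent | Other criteria |
|---|---|---|---|
| Treated parenchymal metastases, stable, off steroids at least 7 days | Excluded | Eligible | – |
| Treated, but unstable or on steroids | Not excluded by item 1 | Not eligible (implied by the condition) | Item 7, discretionary |
| Untreated parenchymal metastases | Not addressed | Not addressed | Item 7, discretionary |
| Symptomatic leptomeningeal disease | – | – | Excluded by item 2 |
| Asymptomatic leptomeningeal disease | – | – | Allowed by item 2 |

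Items 2, 5 and 6 each state an exclusion and then a carve-out. Item 1 has only the carve-out. Section 4.4.5 mandates the scan but attaches no eligibility consequence to its result.

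**2. ANC thresholds.** The units are equivalent: 1 cell/µL = 1 cell/mm³.

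- Entry (inclusion 7a): ANC ≥ 1000.
- Dosing (Table 13): not at ANC ≤ 1500.
- Overlap: 1000 ≤ ANC ≤ 1500 passes the first rule and fails the second.

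Because section 4.4 accepts a laboratory result up to 14 days old for Cycle 1, a screening value inside this band can also serve as the pre-dose value. No passage exempts Cycle 1 Day 1 from Table 13 or applies Table 13 to it.

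**3. Effect on the design (illustration).** Inputs from section 3.1.3: 9 patients in stage 1, stop at 0 responses; 8 more in stage 2; reject at 3 or more responses; null rate 5%, alternative 25%. With n1 and n2 the stage sizes:

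P(reject) = P(X ≥ 3 of n1 + n2) − P(0 of n1) × P(X ≥ 3 of n2)

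The plan's own figures reproduce:

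- At 25%: 0.8363 − 0.0751 × 0.3215 = 0.812 (stated power 81.2%).
- At 5%: 0.0503 − 0.6302 × 0.0058 = 0.047 (stated type I error 4.7%).

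Now assume that some accrued patients are never dosed and not replaced, and that the rule of 3 responses is kept:

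| Dosed (stage 1 + stage 2) | Power at 25% | Type I error at 5% |
|---|---|---|
| 9 + 8 | 0.812 | 0.047 |
| 9 + 7 | 0.8029 − 0.0751 × 0.2436 = 0.785 | 0.041 |
| 9 + 6 | 0.7639 − 0.0751 × 0.1694 = 0.751 | 0.035 |
| 8 + 8 | 0.8029 − 0.1001 × 0.3215 = 0.771 | 0.039 |

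The documents do not say how many patients would have an ANC in the overlap or untreated CNS metastases.

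**The case against.** The strongest reply is that competent readers will not be misled.

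- **Intent of item 1.** A reader might infer that item 1, read sympathetically, excludes nobody and so opens the trial to all CNS disease. The documents do not support that. The condition in item 1 implies that treated patients who are unstable or on steroids are out, section 4.4.5 speaks of stable brain metastases, item 2 excludes symptomatic leptomeningeal disease, and item 7 lets an investigator exclude others. What stands is narrower: the inverted wording, and the silence on untreated parenchymal disease, which a discretionary clause softens but does not close.
- **Central review.** Sections 4.6.1 and 4.6.2 require the study principal investigator and the consortium office to confirm eligibility before therapy starts. This limits divergence between sites, but the reviewers apply the same text.
- **Scope of Table 13.** A reader might infer that a patient with an ANC of 1000 to 1500 cannot receive the first dose. That is too absolute. The line is a recommendation in a neutropenia row, within guidance on suspected MGC018-related toxicity, and an undosed patient has no such toxicity. Section 4.4 gives no number for an acceptable value, and the count may recover after screening. Yet the Table 13 line carries no such limit itself, and section 4.4 covers every dose, so the ambiguity remains.
- **Replacement.** Section 4.5.1 rules out replacement only for patients who received at least one cycle, and section 4.5.2 for those who withdraw from the study. An undosed patient need be neither. If such patients are replaced, 17 are dosed and power stays at 81.2%.

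**Conclusion.** The point holds for two rules. Item 1 is mis-drafted in a binding criterion, and the handling of untreated parenchymal CNS metastases is undefined. The ANC thresholds for entry and dosing differ over 1000 to 1500, and the text does not say which applies at Cycle 1 Day 1. Both conclusions follow from the wording alone and need no assumption about patient numbers.

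The statistical effect is secondary. A reader might take 78.5% or 75.1% as the trial's expected power. These figures hold only if one or two stage-2 patients are accrued, never dosed and not replaced, and the documents establish none of these conditions.

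The missing INR/aPTT entry in the calendar is clerical, since inclusion 7g and section 4.4.6 already require the tests.

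**What to change.** 1. Rewrite exclusion item 1 as the condition that excludes a patient. State explicitly how untreated and symptomatic parenchymal CNS metastases are handled, consistent with the head imaging and follow-up in section 4.4.5.
2. Reconcile inclusion 7a, the Table 13 neutropenia line and the pre-dose laboratory rule in section 4.4, and say whether Table 13 applies to Cycle 1 Day 1. Which ANC value and which CNS rule to adopt are clinical decisions for the sponsor, and this review takes no position on them.
3. Add INR and aPTT to the laboratory row of Appendix 1, Table 1.

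The cost is amendment wording and the associated approval. Depending on the sponsor's choices, a few patients may become ineligible. The sample size and the decision rule need no change.
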